## **12.4 Monitoring Guidelines (Study Stopping Rule Events)**

During the CRM, the trial will stop if the posterior probability that the lowest dose is more toxic than the target is greater than 90%.

After the MTD has been established stopping rules will also be employed to monitor excess toxicity outside of the Phase I trial.

Meeting either stopping rule criteria temporarily will halt enrollment per [Section 10.4](#).

**(1) Grade 4-5 non-hematologic, non-relapse, non-infectious toxicity (except fever) by 42 days after the start of the first GTB-3550 TriKE treatment block:** We will construct a boundary such that the probability of early stopping is at most 10% if the toxicity rate is equal to 10%. Assuming 27 additional patients are enrolled after phase I, the upper stopping boundary for toxicity would be 2/3, 3/8, 4/13, 5/20, 6/26 or 7 events.

**(2) Non-relapse, non-infectious treatment related mortality** within 60 days of starting GTB-3550 TriKE treatment: Assuming the same parameters as in (1), the upper stopping boundary for TRM will be 2/3, 3/8, 4/13, 5/20, 6/26 or 7 events. If the true rates of both toxicity and TRM are 30%, the probability of early stopping will be 88% for each guideline.

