### 12.3 Sample Size Justification

## Trial Size Determination:

Assuming a target DLT probability of 20%, an effect size or odds ratio of 1.7 and a commonly used accuracy index of 0.5, the initial sample size is 27. We conservatively rounded to 30 patients.

Operating characteristics for various 'true' probabilities are listed in [Table 1](#).

Table 1.

If fewer than 14 patients are enrolled at the MTD, the Phase II extension trial using the Simon's two-stage design will require 30 patients to test the null hypothesis that the response rate is <20% versus the alternative that the response rate is  $\geq 40\%$  after assuming 80% power and a significance level of 0.05.

If the Phase I trial enrolls more than 13 patients at the MTD, we will adjust the futility rule of the two-stage design while maintaining the constraints of 80% power, a significance level of 0.05 and using a maximum of 30 patients. We will choose the rule that minimizes the expected sample size given a true response rate equivalent to the null hypothesis. We expect that approximately 44 patients will be required due to use of patients from the Phase I trial in the Phase II extension but the sample size may be as high as 57. Enrollment is expected to be 1-2 patients per month.

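### The 88% stopping probability in Section 12.4 belongs to the maximum of 27 patients after Phase I; for the roughly 14 the plan expects, the printed boundary gives 64%

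*Combined protocol and SAP*

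**What the plan says.** Section 12.4 explains that, once the MTD is established, "stopping rules will also be employed to monitor excess toxicity outside of the Phase I trial". Section 10.4 likewise confines these rules to the Phase II expansion. The design criterion is that "the probability of early stopping is at most 10% if the toxicity rate is equal to 10"%. Then, "Assuming 27 additional patients are enrolled after phase I", "the upper stopping boundary for toxicity would be 2/3, 3/8, 4/13, 5/20, 6/26 or 7 events". The mortality guideline uses the same parameters and the same boundary. One figure is given at an unacceptable rate: "If the true rates of both toxicity and TRM are 30%, the probability of early stopping will be 88% for each guideline".

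Section 12.3 gives the numbers that determine how many patients the rule will see. For Phase I: "We conservatively rounded to 30 patients". For the whole trial: "We expect that approximately 44 patients will be required due to use of patients from the Phase I trial", with 57 as the upper limit. The total is below 30 + 30 because patients treated at the MTD in Phase I count toward the 30 in Phase II (Section 12.1, Phase II Extension). No stopping probability is given for the expected total.

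**The concern.** The operating characteristic in Section 12.4 and the expected sample size in Section 12.3 describe different trials. A safety reviewer reading Section 12.4 will take 88% as the protection that each rule offers, because it is the only figure of its kind in the plan. It applies only if almost no Phase I patients were treated at the MTD. The more of the Phase II sample that comes from Phase I, the fewer patients the rule watches and the less often it can trigger. What is at stake is how well the plan describes its two Phase II safety rules in the case it considers most likely.

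**Working it through.** **Inputs**
- Phase I size 30, expected total about 44, maximum total 57 (Section 12.3).
- Boundary (Section 12.4): stop at 2 events by patient 3, 3 by patient 8, 4 by patient 13, 5 by patient 20, 6 by patient 26, or 7 events.
- Scope: patients enrolled after Phase I (Sections 10.4 and 12.4).

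**Patients under the rule**
- Maximum: 57 − 30 = 27, which is exactly the number assumed in Section 12.4.
- Expected: 44 − 30 = about 14. The plan does not print this figure; it follows by subtraction. It implies 30 − 14 = about 16 Phase I patients at the MTD who count for efficacy but not for this rule.

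**Method.** Exact binomial recursion, patient by patient. Carry the probability of each event count among trials not yet stopped, and remove the paths that reach the limit in force.

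**Reproducing the plan.** For 27 patients the recursion gives 87.8% at a true 30% rate (plan: 88%) and 9.7% at 10% (plan: at most 10%). Both agree.

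**Same boundary, 14 patients, true rate 30%**
1. Patients 1-3, stop at 2 events: P(at least 2 of 3) = 0.216. Continuing: 0 events 0.343, 1 event 0.441.
2. Patients 4-8, stop at 3 in total: 0.343 × P(at least 3 of 5) + 0.441 × P(at least 2 of 5) = 0.343 × 0.163 + 0.441 × 0.472 = 0.264. Cumulative 0.480. Continuing: 0 events 0.058, 1 event 0.198, 2 events 0.265.
3. Patients 9-13, stop at 4 in total: 0.058 × 0.031 + 0.198 × 0.163 + 0.265 × 0.472 = 0.159. Cumulative 0.639.
4. Patient 14: the limit is now 5 and at most 3 events have occurred, so stopping is impossible. The total stays at 0.639.

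At a 10% rate the same steps give 0.028, 0.054 and 0.068.

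**Boundary rebuilt for 14 patients.** A constant-level (Pocock-type) search with at most 10% stopping at a 10% rate gives 2 by patient 4, 3 by patient 9, 4 by patient 14. Cumulative stopping is 0.052, 0.082, 0.097 at a 10% rate and 0.348, 0.582, 0.713 at a 30% rate.

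| Patients after Phase I | Boundary | Stop at 10% | Stop at 30% | Miss at 30% |
|---|---|---|---|---|
| 27 (maximum) | printed | 9.7% | 88% | 12% |
| 14 (expected) | printed | 6.8% | 64% | 36% |
| 14 (expected) | rebuilt | 9.7% | 71% | 29% |

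At a true 20% rate the printed boundary stops with probability 52% for 27 patients and 32% for 14. Testing only at the listed patient numbers, rather than after every patient, gives the same 10% and 30% results at 14 and at 27.

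**The case against.** The strongest reply is that nothing here is miscalculated. Section 12.4 states its 27-patient assumption and the 88% reproduces under it. A reader might infer an arithmetic error, or a claim that 88% holds for 14 patients; the documents support neither, since they say nothing about 14. This stands in full: the gap is an omitted scenario.

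Second, the wording leaves room to adapt. The text speaks of a boundary still to be constructed and puts the toxicity list in the conditional. The mortality list is worded more firmly, but on the same parameters. So 64% supposes that the printed list is kept. This also stands, but the plan nowhere says that the boundary will be recomputed, and a recomputed one still reaches only 71%.

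Third, the limits for the first 13 patients are identical in both cases. The probability falls because enrolment ends sooner, and fewer patients are exposed: at a true 30% rate, about 9.3 treated after Phase I on average against 12.3. That is fair context. It does not make 88% the right description of the expected case.

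Two further inferences should be resisted. Using 6.8% of the permitted 10% is not a breach, because the criterion is an upper limit. Nor are Phase I patients at the MTD unmonitored: the DLT definition, the CRM updating and the lowest-dose stopping rule cover them, though over 28 days rather than 42 or 60. Keeping them outside the Phase II rule is an explicit design choice.

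Finally, crossing a boundary only halts enrolment temporarily for review by the investigator and sponsor (Section 10.4), and no efficacy conclusion depends on it. That limits the consequence.

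**Conclusion.** The point holds as a gap in reporting and specification. The 88% is correct at maximum enrolment. In the plan's own expected case each rule stops with probability 64% at a true 30% rate under the printed boundary, so the chance of missing such a rate is 36% against 12%, about three times as high. Rebuilding the boundary under the plan's constraint recovers part of this, to 71%.

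The result rests on four assumptions: about 14 patients after Phase I, derived from an approximate total of 44; Phase I patients excluded from the count; independent patients with a constant event rate; and enrolment not cut short by the futility rule. The expected number is not exact, and the figure moves with it: with the printed boundary checked after each patient, 13 patients also give 64%, 17 give 71% and 20 give 80% at a 30% rate. All are below 88%.

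**What to change.** In Section 12.4:
1. Label 88% as the value at maximum enrolment (27 patients after Phase I).
2. Beside it, give the value for the expected number: about 64% at a 30% rate and 6.8% at a 10% rate, for 14 patients and the printed boundary.
3. State that, once the MTD is known, the boundary will be recomputed under the same 10% constraint for the actual number of patients remaining. As an illustration for 14 patients, 2/4, 3/9, 4/14 gives 9.7% at a 10% rate and 71% at a 30% rate.

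The cost is one recalculation, a few changed sentences and a less favourable stated figure. Treatment, eligibility and sample size are unaffected.

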## **13 Conduct of the Study**

### **13.1 Good Clinical Practice**

The study will be conducted in accordance with the appropriate regulatory requirement(s). Essential clinical documents will be maintained to demonstrate the validity of the study and the integrity of the data collected. Master files should be established at the beginning of the study, maintained for the duration of the study and retained according to the appropriate regulations.

### **13.2 Ethical Considerations**

The study will be conducted in accordance with ethical principles founded in the Declaration of Helsinki. The IRB will review all appropriate study documentation in order to safeguard the rights, safety and well-being of the patients. The study will only be conducted at sites where IRB approval has been obtained. The protocol, consent, written information given to the patients, safety updates, annual progress reports, and any revisions to these documents will be provided to the IRB by the investigator.

### **13.3 Informed Consent**

All potential study participants will be given a copy of the IRB-approved consent to review. The investigator or designee will explain all aspects of the study in lay language and answer all questions regarding the study. If the participant decides to participate in the study, he/she will be asked to sign and date the consent document. Patients who refuse to participate or who withdraw from the study will be treated without prejudice.

## Appendix I - Karnofsky Performance Status

Karnofsky Performance Scale	
Percent	Description
100	Normal, no complaints, no evidence of disease.
90	Able to carry on normal activity; minor signs or symptoms of disease.
80	Normal activity with effort; some signs or symptoms of disease.
70	Cares for self, unable to carry on normal activity or to do active work.
60	Requires occasional assistance, but is able to care for most of his/her needs.
50	Requires considerable assistance and frequent medical care.
40	Disabled, requires special care and assistance.
30	Severely disabled, hospitalization indicated. Death not imminent.
20	Very sick, hospitalization indicated. Death not imminent.
10	Moribund, fatal processes progressing rapidly.
0	Dead.

## Appendix II - Revised International Prognostic Scoring System (IPSS-R) for Myelodysplastic Syndromes and Risk Assessment Calculator Link

Developed by the International Working Group for the Prognosis of MDS (IWG-PM) under the aegis of the MDS Foundation, Inc.

<https://www.mds-foundation.org/ipss-r-calculator/>

### IPSS-R Cytogenetic Risk Groups\*,\*\*

Cytogenetic prognostic subgroups	Cytogenetic abnormalities
Very good	-Y, del(11q)
Good	Normal, del(5q), del(12p), del(20q), double including del(5q)
Intermediate	del(7q), +8, +19, i(17q), any other single or double independent clones
Poor	-7, inv(3)/t(3q)/del(3q), double including -7/del(7q), Complex: 3 abnormalities
Very poor	Complex: >3 abnormalities

### IPSS-R Prognostic Score Values\*

Prognostic variable	0	0.5	1	1.5	2	3	4
Cytogenetics	Very Good		Good		Intermediate	Poor	Very Poor
BM Blast %	≤2		>2- <5%		5-10%	>10%	
Hemoglobin	≥10		8-10	<8			
Platelets	≥100	50- <100	<50				
ANC	≥0.8	<0.8					

**IPSS-R Prognostic Risk Categories/Scores\***

RISK CATEGORY	RISK SCORE
Very Low	$\leq 1.5$
Low	$>1.5 - 3$
Intermediate	$>3 - 4.5$
High	$>4.5 - 6$
Very High	$>6$

\*Greenberg, Tuechler, Schanz et al, Revised International Prognostic Scoring System (IPSS-R) for Myelodysplastic Syndrome, Blood 120: 2454, 2012

\*\*Schanz J et al, J Clin Oncology 2012; 30:820.

## Appendix III - Response Criteria

### **Acute Leukemias:**

- **Morphologic complete remission (CR):** ANC  $\geq$  1,000/mcl, platelet count  $\geq$  100,000/mcl, < 5% bone marrow blasts, no Auer rods, no evidence of extramedullary disease. (No requirements for marrow cellularity, hemoglobin concentration).
- **Morphologic complete remission with incomplete platelet recovery (CRp):** Same as CR platelet count < 100,000/mcl.
- **Morphologic complete remission with incomplete blood count recovery (CRI):** Same as CR but ANC may be < 1,000/mcl and/or platelet count < 100,000/mcl.
- **Partial remission (PR):** ANC  $\geq$  1,000/mcl, platelet count > 100,000/mcl, and at least a 50% decrease in the percentage of marrow aspirate blasts to 5-25%, or marrow blasts < 5% with persistent Auer rods.

### **Myelodysplastic Syndromes (MDS):**

Category	Response criteria (responses must last at least 4 wk)
Complete remission	
Bone marrow: <math>\leq</math> 5% myeloblasts with normal maturation of all cell lines*
 
 
• Persistent dysplasia will be noted*†
 
 
Peripheral blood‡
 
 
• Hgb <math>\geq</math> 11 g/dL
 
• Platelets <math>\geq</math> 100 <math>\times</math> 10^9/L
 
• Neutrophils <math>\geq</math> 1.0 <math>\times</math> 10^9/L†
 
• Blasts 0%
 

Partial remission	
All CR criteria if abnormal before treatment except:
 
 
• Bone marrow blasts decreased by <math>\geq</math> 50% over pretreatment but still <math>></math> 5%
 
 
Cellularity and morphology not relevant

Marrow CR	
Bone marrow: <math>\leq</math> 5% myeloblasts and decrease by <math>\geq</math> 50% over pretreatment†
 
Peripheral blood: if HI responses, they will be noted in addition to marrow CR†

Stable disease	
Failure to achieve at least PR, but no evidence of progression for <math>\geq</math> 8 weeks

Cytogenetic response	
Complete
 
 
• Disappearance of the chromosomal abnormality without appearance of new ones
 
 
Partial
 
 
• At least 50% reduction of the chromosomal abnormality
 

Hematologic Improvement	
Erythroid response (pretreatment, < 11 g/dL): Hgb increase by 1.5 g/dL Relevant reduction of units of RBC transfusions by an absolute number of at least 4 RBC transfusions/8 wk compared with the pretreatment transfusion number in the previous 8 wk.
 
Platelet response (pretreatment, < 100 X 10^9/L): Absolute increase of < 30 X 10^9/L for patients starting with 20 X 10^9/L platelets Increase from less than 20 X 10^9/L to greater than 20 X 10^9/L and by at least 100%
 
Neutrophil response (pretreatment, < 1.0 X 10^9/L) At least 100% increase and an absolute increase 0.5109/L

MDS indicates myelodysplastic syndromes; Hgb, hemoglobin; CR, complete remission; HI, hematologic improvement; PR, partial remission; FAB, French-American-British; AML, acute myeloid leukemia; PFS, progression-free survival; DFS, disease-free survival.

\*Dysplastic changes should consider the normal range of dysplastic changes (modification).

†Modification to IWG response criteria.

‡In some circumstances, protocol therapy may require the initiation of further treatment (eg, consolidation, maintenance) before the 4-week period. Such patients can be included in the response category into which they fit at the time the therapy is started. Transient cytopenias during repeated chemotherapy courses should not be considered as interrupting durability of response, as long as they recover to the improved counts of the previous course.

Ref: Cheson BD, Greenberg DL, Bennett JM, et al. Clinical application and proposal for modification of the International Working Group (IWG) response criteria in myelodysplasia. *Blood*. 2006;108:419-425.

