**Extended Phase II Component:**

Patients will receive three consecutive blocks of four 24 hour continuous infusions of GTB-3550 TriKE at the Phase I MTD separated by a 72 hour rest. There is no staggering of enrollment for this component.

**Stage 1:** Enroll a total of 13 patients (including all treated at the MTD in Phase I). If 3 or more of these patients have clinical response by Day 42 the trial will continue to Stage 2. If the Phase I component enrolls more than 13 patients at the MTD, the futility rule for the two-stage design will be adjusted with the given number of patients enrolled at the MTD.

**Stage 2:** Enroll an additional 17 patients. If 10 of 30 patients have a clinical response by Day 42, GTB-3550 TriKE will be considered promising for further investigation.

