## 1 Objectives

### 1.1 Primary Objective

Phase I Dose Finding: To identify the maximum tolerated dose (MTD) of GTB-3550 TriKE defined as the dose level that most closely corresponds to a dose limiting toxicity rate (DLT) of 20%.

Phase II Extension: To determine preliminary efficacy as measured by the rates of “best” clinical response by Day 42 after the start of the 1st infusion.

For AML clinical response includes complete remission with or without hematologic or platelet recovery (CR, CRi or CRp) or partial response. For MDS clinical response includes complete remission, marrow CR (with incomplete peripheral blood count normalization), partial response or hematologic improvement (HI). For advanced systemic mastocytosis response is considered a decrease in mast cell burden in bone marrow or serum tryptase level by at least 30%.

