## 4 Study Design

This is a multisite Phase I/II clinical trial of GTB-3550 (CD16/IL-15/CD33) tri-specific killer cell engager (TriKE) for the treatment of CD33-expressing high risk myelodysplastic syndromes, refractory/relapsed acute myeloid leukemia or advanced systemic mastocytosis. Up to 10 study centers may take part in this trial.

Patients receive a single course of GTB-3550 TriKE given as 3 weekly treatment blocks. Each block consists of four consecutive 24 hour continuous infusions of GTB-3550 TriKE followed by a 72 hour break after Block #1 and #2. All treatment is given as an inpatient.

Toxicities are monitored through Day 28 (as assessed on Day 29) with continued toxicity assessment through Day 60. Disease response is assessed by bone marrow biopsy performed between Day 21 and 42 after the start of the 1st infusion. Follow-up for response and survival continues through 6 months from study treatment start.

The study consists of two components. The dose finding component is a modified version of a Phase I trial and the extended component is a modified Phase II trial.

**Dose Finding Component:** The Phase I component uses a continual reassessment method (CRM) to determine the maximum tolerated dose (MTD) of GTB-3550 TriKE. Up to 7 doses levels will be tested. The goal of the CRM is to identify the dose level which most closely corresponds to the targeted dose limiting toxicity (DLT) rate of 20%.

Patients are enrolled in cohorts of 2 beginning at Dose Level 1. A minimum of 1 week must separate each patient. Both patients within a cohort must reach Day 28 (end of the DLT assessment period) prior to enrollment of a subsequent cohort. The study statistician assigns each new cohort of 2 patients to the most appropriate dose level based on updated toxicity probabilities. As enrollment proceeds, each cohort is assigned to an increased, decreased or equivalent dose level based on prior data in the trial until the study sample reaches 30. At this time, the last dose is declared the MTD and the GTB-3550 TriKE dose for the extended component.

**Extended Component:** The primary goal of the extended component is to study the potential efficacy of GTB-3550 TriKE in this patient population. Efficacy is measured using rates of complete and partial remission. A Simon's MiniMax two-stage design is used in this phase. Monitoring guidelines are in place to stop the study early for excessive toxicity.

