## 12 Statistical Considerations

### 12.1 Study Design and Endpoints

This is a multisite Phase I/II study of GTB-3550 trispecific killer cell engager (TriKE) for the treatment of high risk MDS and relapsed AML. Once the MTD is identified, the objective will be to confirm safety and obtain preliminary estimates of efficacy as measured by the objective response, the **primary trial endpoint** as assessed between Day 21 and Day 42. For AML clinical response includes complete remission with or without hematologic or platelet recovery (CR, CRi or CRp) or partial response. For MDS clinical response includes complete remission, marrow CR (with incomplete peripheral blood count normalization), partial response or hematologic improvement (HI). For advanced systemic mastocytosis response is considered a decrease in mast cell burden in bone marrow or serum tryptase level by at least 30%.

All patients completing Block #1 will be evaluable for DLTs and toxicities. Patients who discontinue therapy prior to completion of both Block #1 and Block #2 will be replaced. Patients completing Block #1 and Block #2, but come off treatment for disease progression, will still be evaluable for efficacy and will not be replaced. If needed a subgroup of patients receiving all 3 blocks will also be evaluated for response as a secondary population. We expect that the number of patients coming off therapy after only completing block #1 will be minimal.

**Secondary trial endpoints** will include toxicity through Day 29 and overall survival (OS) at 6 months from 1st dose of study drug.

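### Does the 4-week duration rule for MDS responses conflict with a Phase II endpoint counted by Day 42?

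*Combined protocol and SAP*

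**What the plan says.** - **Endpoint.** Section 1.1 sets the Phase II objective as best "clinical response by Day 42 after the start of the" first infusion. Section 12.1 describes the objective response "as assessed between Day 21 and Day 42". For MDS it counts CR, marrow CR, PR and hematologic improvement (HI).
- **Decision rule.** In the Study Schema, if 3 or more of 13 patients "have clinical response by Day 42 the trial will continue to Stage 2". The final rule reads "If 10 of 30 patients have a clinical response by Day 42", and the drug is then considered promising.
- **MDS criteria.** The Appendix III table heading adds "responses must last at least 4 wk". One HI criterion is a transfusion reduction of "at least 4 RBC transfusions/8 wk compared with the pretreatment transfusion number in the previous 8 wk". A footnote deals with further treatment begun before the 4 weeks are complete: "Such patients can be included in the response category into which they fit at the time the therapy is started". The AML criteria carry no duration rule, and none is stated for mastocytosis.
- **Assessments.** Section 8.1 schedules one post-treatment marrow, between Day 21 and Day 42. CBCs are scheduled at each block start, daily during infusions, and on Days 22, 29 and 60. It also marks response assessment in follow-up until relapse, progression or new therapy.
- **Follow-up.** Section 4 states: "Follow-up for response and survival continues through 6 months from study treatment start". The opening of Section 8 says that follow-up disease status is taken from the medical record. Section 7.6 mentions only overall survival for follow-up.

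**The concern.** A response that must last 4 weeks and a count taken at Day 42 do not fit together if both are applied literally, because the first response marrow cannot be earlier than Day 21. Two people scoring the same MDS patient could disagree, and with thresholds as small as 3 of 13 and 10 of 30 one patient can change the decision. The date on which the counts become final is also unstated: Day 42, or as late as Day 70. Sections 12.1 to 12.3 do not mention the 4-week condition. If MDS responses were in fact discarded, the trial could miss an active drug.

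**Working it through.** **1. Day counts**

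Inputs: 28 days and 8 weeks (Appendix III); Day 21 to 42 marrow and Day 60 ± 7 visit (Section 8.1); last infusion of Block 3 ending on Day 19 (Section 10.2); re-treatment 2 to 4 weeks after the first course (Section 7.4).

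- Latest onset that completes 28 days by Day 42: 42 − 28 = Day 14.
- Marrow response first seen on Day 21 or Day 42: 21 + 28 = Day 49; 42 + 28 = Day 70.
- Count-based HI seen on the Day 12 CBC: 12 + 28 = Day 40, inside the window. Seen on Day 22 or 29: Day 50 or 57, both before the nominal Day 60 CBC.
- Latest onset for which the Day 60 CBC falls at least 28 days later: 60 − 28 = Day 32, or 67 − 28 = Day 39 at the end of the visit window.
- The 8-week transfusion comparison ends no earlier than 1 + 56 = Day 57.
- Re-treatment can begin on 19 + 14 = Day 33 to 19 + 28 = Day 47 without block delays, before Day 49.

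**2. The plan's own power**

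P(go) = Σ over x = 3 to 13 of P(X₁ = x) · P(X₂ ≥ 10 − x), with X₁ ~ Bin(13, p) and X₂ ~ Bin(17, p).

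At p = 0.40, P(go) = 0.8051, which agrees with the 80% in Section 12.3. At p = 0.20, P(go) = 0.0577. That this exceeds the stated 0.05 is a separate matter and plays no part here.

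**3. If the 4 weeks had to end by Day 42**

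The documents give no MDS share, so f = 10% or 25% is assumed, with the same 40% true rate in every disease. If a fraction q of MDS responses is not counted, p = 0.4 × (1 − f·q).

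| MDS share f | Fraction lost q | p | P(go) |
|---|---|---|---|
| 10% | 50% | 0.38 | 74.0% |
| 10% | 100% | 0.36 | 66.4% |
| 25% | 50% | 0.35 | 62.2% |
| 25% | 100% | 0.30 | 39.4% |

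The 100% rows are upper bounds on the loss, because a count-based HI present by Day 14 can still qualify.

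**4. If the response is reached by Day 42 and duration is checked later**

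No response that lasts is lost. If the 40% alternative refers to responses as Appendix III defines them, short-lived ones were never part of it, so p stays at 0.40 and P(go) at 80.5%. A lower figure appears only if 40% is taken to be the rate before the duration check. With 10% or 25% of MDS responses not lasting (assumed), P(go) would then be 79.3% or 77.4% at f = 10%, and 77.4% or 72.2% at f = 25%. That drop reflects the definition of response, not the unwritten timing.

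**5. If duration were removed from the count**

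Suppose short-lived count rises add a = 5 or 10 points to the MDS rate (assumed) when the true rate is 20%. Then p = 0.20 + f·a.

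| f | a | p | P(go) |
|---|---|---|---|
| 10% | 5 points | 0.205 | 6.7% |
| 10% | 10 points | 0.21 | 7.6% |
| 25% | 5 points | 0.2125 | 8.1% |
| 25% | 10 points | 0.225 | 11.1% |

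The false-go probability rises from 5.8%, so dropping the 4-week rule to make the timing tidy has its own cost.

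**The case for a change.** The strongest case for acting is that no sentence states the later-check reading. Follow-up to 6 months makes such a check possible, but nothing says that it confirms or reverses a Day 42 response. The details are also incomplete:

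- No marrow is scheduled after the Day 21 to 42 one. The Day 60 aspirate in Section 8.2 is only an alternative time for the same research sample, so a marrow CR can be rechecked only if a marrow is done in routine care.
- The Day 60 CBC comes too early for a response first seen after Day 32 (Day 39 at the latest visit), so those cases rest on the medical record.
- Re-treatment may start before 4 weeks and is outside the statistical analysis. The footnote marker sits on the CR blood counts, which reaches PR through the CR criteria but does not clearly reach marrow CR or HI.
- The 8-week transfusion criterion cannot be met by Day 42.

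These points stand as facts, but they concern a few MDS patients at most and leave the meaning of the endpoint intact. Section 7.6's silence on response follow-up does not exclude it, since Sections 4, 8 and 8.1 provide for it. The different standards across diseases come with disease-specific response criteria.

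**Conclusion.** The gap is real but small, and no change to the plan is needed. The literal reading would make CR, PR and marrow CR first seen on the scheduled marrow uncountable in MDS, although Sections 1.1 and 12.1 list them as responses. An analyst would therefore take Day 42 as the date by which the response is reached and look for loss of response over the next 4 weeks in the Day 60 CBC and the follow-up disease status. Patients who start further treatment sooner would keep the category held at that time, as the footnote suggests. On that reading exact power remains 80.5%, so no loss of power should be claimed.

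This rests on two assumptions: that the later check is the intended reading, and that the 40% alternative refers to responses as Appendix III defines them. The effect is confined to MDS, one of three diseases, whose share is not given. Writing the timing down would only record what a sensible analyst would do anyway and would not by itself settle marrow CR or early re-treatment. Taking duration out of the count would be a debatable change of endpoint and, on the assumed figures, could raise the false-go probability from 5.8% to as much as 11.1%.
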